Study Title: Combined Smoking Cessation and Cognitive Processing Therapy for PTSD

Clinical Trials Identifier: NCT01901848

Protocol and Statistical Analysis Plan, 1/9/2017

Title: Combined Smoking Cessation and Cognitive Processing Therapy for PTSD

Background: The present study seeks to gather data to determine the efficacy of a smoking cessation intervention implemented as part of individual cognitive processing therapy (CPT) for the treatment of posttraumatic stress disorder (PTSD). CPT is based on a social cognitive theory of PTSD that includes primary emotional responses to traumatic events such as fear, anger, and sadness, as well as secondary emotions resulting from a patient's faulty interpretations of the traumatic event. CPT addresses PTSD by facilitating affective expression so that affective components of the trauma memory can be altered. In addition, faulty beliefs about the trauma are challenged and modified using Socratic questioning.

A number of studies of CPT have provided empirical supported of its efficacy in reducing PTSD symptoms (Monson, et al., 2006). Consequently, recent VA guidelines mandating that patients have access to empirically supported treatments have led to CPT being broadly implemented within the VA system. The original CPT protocol devoted a portion of the intervention to patients writing descriptions of their traumatic events to be read both during and outside treatment sessions. An alternative version of the protocol removes the written trauma accounts while retaining the cognitive processing component (Cognitive Processing Therapy – Cognitive version; CPT-C). A recent dismantling study comparing the original CPT protocol to the CPT-C found that the CPT-C was equally effective in reducing PTSD symptoms, and the reduction of PTSD symptoms occurred by the end of session six (Resick, et al., 2008). Individual CPT for PTSD typically consists of 12 sessions that each last 50 minutes. Research suggests that the 12 session protocol is feasible and has a relatively low dropout rate (Resick, et al., 2008). In a personal communication with [name], co-developer of CPT, she suggested that the study utilize the 12-session CPT-C protocol. Based on this suggestion, and because the 12-session protocol is most often used by clinicians in the VA system and is evidence-based, we plan to utilize the 12-session CPT-C protocol.

In addition to the symptoms of PTSD, several problems are frequently comorbid with PTSD. Among these, one prominent problem associated with significant medical morbidity is cigarette smoking. Many veterans with PTSD smoke cigarettes. Epidemiological data indicate that 45% of those with PTSD smoke cigarettes (Lasser, et al., 2000). Although smoking is prevalent in veterans with PTSD, many report interest in quitting smoking, with one recent study indicating that, at the time of assessment, 50% of smokers were contemplating quitting smoking and another 21% were preparing to make a quit attempt (Kirby, et al., 2008). Approaches to improving care and access to care for smokers with PTSD may be particularly useful considering the tendency for psychiatric groups to be socially isolated (Schroeder, 2008) and undertreated for smoking cessation (Prochaska & Velicer, 2004). By integrating smoking cessation interventions with mental health treatment, a greater proportion of those with psychiatric illness will receive treatment and quit smoking. In addition, research suggests that PTSD symptoms are related to smoking behavior ([name], et al., 2005).

Despite this connection, interventions seeking to assist people with PTSD in smoking cessation have not traditionally targeted PTSD symptom reduction. Integration of smoking cessation with PTSD treatment could reduce symptoms and provide patients with strategies for managing symptoms without using cigarettes.

In order to adequately examine the unique effects of CPT-C combined with integrated smoking cessation care, we will utilize a randomized controlled trial design. Both interventions will employ extensive smoking cessation treatment, including counseling, pharmacotherapy, and text messaging (described below) to assist in the quit attempt. One group will be randomized to receive CPT-C alongside the smoking cessation intervention. The other group will be offered to have 12 sessions of CPC-C post participation in the active smoking cessation portion of the study.

## **Objectives:**

The primary aim of the proposed study is to evaluate the integration of CPT-C and smoking cessation treatment in an individual 12-session PTSD protocol as compared to a protocol including the same smoking cessation treatment for individuals with PTSD, but without CPT-C. This intervention will be evaluated with the following hypotheses:

- Compared to the smoking cessation alone protocol, the smoking cessation + concurrent CPT-C protocol will result in reduced frequency and intensity of PTSD symptoms.
- 2) Compared to the smoking cessation alone protocol, the smoking cessation + concurrent CPT-C protocol will result in reduced depressive symptoms.
- 3) The smoking cessation + concurrent CPT-C protocol will result in decreased smoking rates, relative to published data on VA smoking cessation usual care.
- 4) Greater PTSD symptom reduction during the smoking cessation + concurrent CPT-C treatment will result in longer duration to smoking lapse and relapse.
- 5) Exploratory research question: Will use of automated text messaging as an adjunct to smoking cessation be feasible, and will it impact quit rates?

### Methods:

Recruitment

Participants will be recruited from among outpatients at the Durham VAMC clinics, including OEF/OIF/OND program, Access Clinic, Women's Health Clinic, Primary Health Care and PTSD Clinics. Participants will be recruited through IRB approved flyers, brochures, and letters advertising a study on PTSD and smoking cessation posted in the VA Medical Center. We will place IRB-approved recruitment materials in the community in places such as grocery stores, restaurants, etc. We will also advertise via the closed

circuit television system within the VA Medical Center and in local newspapers and online classified services such as www.craigslist.com. Also, upon approval from the Public Affairs officer, we will host informational tables in the medical center. At these informational tables, IRB-approved recruitment materials from the study (and from other studies run in the Traumatic Stress and Health Research Laboratory) will be made available to interested veterans, and study staff members may be on site to answer questions about the research studies. Study information may also be posted on the Durham VA's Facebook page with approval by the VA Public Affairs Officer. No participants will be consented or screened at these public locations.

In conversations with clinicians from several clinics in DVAMC, we have been provided the feedback that they strongly prefer to provide potential participants' names and contact information. Clinicians have reported that they Veterans often indicate that they prefer that their names and contact information be provided directly to study staff. We'd like to make it easy for interested Veterans to get involved in research, while protected the privacy of those Veterans who are not interested in research. Towards that end, we have developed a system whereby clinicians can more directly identify potentially eligible participants. We will ask that the clinician or provider provide basic information about the study to potentially eligible Veterans; clinicians will be provided IRB-approved recruitment materials to assist this patient education. If the Veteran is interested in learning more about participation, the clinician or provider will provide a "Contact Me" information sheet to the Veteran for him/her to complete. We will request that all "Contact Me" sheets will be completed by the Veteran, not by the provider. The information sheet includes options for contact by the study staff (e.g., send me information, call me, send me information and call me). If any Veteran prefers to receive information by mail, he/she will be sent the IRB-approved recruitment letter. Any Veteran who prefers to receive information by phone will be contacted using the IRB-approved telephone script. This information sheet will provide "...written documentation that the subject is willing to be contacted by telephone about the study," as outlined in VHA Handbook 1200.5. "Contact Me" sheets will be delivered to study staff members via secured means (e.g., internal VA snail mail, encrypted Outlook emails with pdf attachments, personal delivery). Any sheets sent via internal VA mail will be placed inside a sealed and addressed envelope that is THEN put into the snail mail envelope. This plan has been reviewed with local privacy and information security officers.

We will also recruit veterans from the Traumatic Stress and Health Laboratory's "Contact Database," IRB #1080; this database contains information about previous lab study participants who have agreed to be contacted about other studies for which they may qualify. A list of potential veteran participants for receipt of recruitment letters will be obtained by using the VA's Fileman system to produce a list of veteran smokers with PTSD. In addition, we will obtain a list of potentially eligible participants from the VISN 6 Mental Illness Research, Education, and Clinical Center (MIRECC) Post-Deployment Mental Health Data Repository (IRB# 01706). Application to recruit from the Re-Contact

Database of the VISN 6 MIRECC Post-Deployment Mental Health Data Repository will be made to the VISN 6 MIRECC Director ([name]) in accordance with IRB and R&D approved data repository procedures.

As recommended by Dillman, Smith, and Christian (Dillman, Smyth, & Christian, 2009), we will recruit participants by sending a series of four letters to those veterans who are smokers with PTSD who are registered at the Durham VA Medical Center. Based on social exchange theory, Dillman and colleagues recommend that the second letter be sent with a small token of appreciation. This token incentive serves two functions – it will encourage respondents to respond based on the principles of social exchange theory, and more importantly, it will bring additional attention to the request for participation so that it will be more readily considered. As recommended, letter two will be sent with a small selection (i.e., monetary value less than \$2) of commemorative stamps. After participants have received the second letter describing the study in detail, a study coordinator may contact them about participation. This information is included in letter 2. Only veterans who are identified via the VA's Fileman system or the MIRECC repository will be sent letters described above. Study staff members will perform random spot-checks of names and addresses on 50% of all letters prior to mailing. This will capture any sorting error that may have occurred during the preparatory procedures. Any person who contacts the study coordinator for more information about the study (whether it be through flyers, word of mouth, etc.) will be informed about the study using the IRB-approved telephone screen script. Participants who drop out will receive partial reimbursement for the time they donate. Participants will be paid up to \$545 for their complete participation. Study costs will be paid using funds from [name] Sciences Research & Development (CSR&D) Career Development Award. Screening is completed following the endorsement of informed consent and HIPAA form by the participant.

## **Population**

The proposed study will recruit seventy male and female veterans ages 18 to 75 for participation in the CPT-C and smoking cessation treatment. Based on data from other similar clinical trials run in the Traumatic Stress and Health Research Laboratory, we estimate that we will need to recruit 120 participants in order to reach an enrollment goal of at least fifty participants.

Participants will be screened for good health by the study physician. If any participant indicates a medical problem that is a possible contraindication to nicotine replacement therapy (NRT), medical clearance to participate in the study will be obtained from their primary care provider and/or other treating physician (e.g. psychiatrist). If the request is denied or not returned, potential participants will be excluded from the study. We are seeking medical clearance rather than excluding participants based on self-report to ensure that we are not prematurely ruling out participants who may be eligible. We are consulting with their primary physician to determine if the use of NRT is appropriate and safe given their current physical status and medication regimen. This medical consult is

a way to further protect the participant and also give them an opportunity to take part in the study if their physician deems it appropriate and safe. At the initial screening, any participant with a primary care physician and/or psychiatrist external to VA will be asked to sign a release of information allowing us to contact a primary care physician or other treating physician (including psychiatrist when applicable) regarding participation in the study. In the screening session, if a participant indicates a medical problem that is a contraindication to NRT or bupropion, as determined by the study physician, we will contact the physician(s) identified in the signed releases of information. Physician(s) external to VA will be contacted by fax using an approved cover sheet and an IRB approved physician letter. If the physician identified in the release of information is a physician located on site at the Durham VA Medical Center, we will contact the physician via email (as is consistent with existing privacy policies at the medical center). Physicians will be asked to email or fax back their approval of participation to a fax machine located in [name] research laboratory. Only members of the research staff listed on the staff listing for this protocol have access to this fax machine. If the request is not returned within two weeks, the study physician will determine eligibility.

Any participant who will not be stable on their medications for the study period, has a history of myocardial infarction in the past 6 months, has a contraindication to NRT and is unable to get medical clearance from their primary care provider will be excluded. If potential participants use any other forms of nicotine such as cigars, pipes, or chewing tobacco, they will be excluded from participation. For safety and informed consent reasons, fluent conversational English will be required of all participants. Adolescent smoking is a phenomenon worth investigating but given both ethical and feasibility issues, we will not include children or adolescents under age 18 in this study.

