## Summary of Inclusion Exclusion Criteria

To be enrolled in this study, participants must have the following characteristics:

- Veteran
- Be current cigarette smokers of at least ten cigarettes a day.
- Meet criteria for current PTSD.
- Speak and write fluent conversational English.
- Be between 18 and 75 years of age.
- Be willing to attempt smoking cessation.

Potential participants will be excluded from participating in this study for the following reasons:

- Screened participants will not be stable on their medications for the study period
- Screened participants who have a history of myocardial infarction in the past 6 months
- Screened participants who have a contraindication to NRT and are unable to get medical clearance from their primary care provider will be excluded.

- Screened participants who use any other forms of tobacco such as cigars, pipes, or chewing tobacco and are unwilling to stop using.
- Pregnancy
- Inability to complete study measures and tasks independently
- Dementia or other brain disorder, schizophrenia, current manic syndrome, or substance abuse/dependence in the preceding 3 months.
- Currently receiving trauma-focused psychotherapy.
- Currently enrolled in another smoking cessation trial.
- Currently living in court-ordered residential substance abuse treatment.

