#### Intervention Protocol

If screened potential participants are deemed eligible to participate in the study, participants will be randomized to participate in either a 12-session CPT-C with concurrent smoking cessation treatment or a smoking cessation treatment including 6 individual smoking counseling sessions, to be followed (if desired) by CPT-C six months after the quit date. Both arms of the study will include text messaging to support the quit attempt (smokefree VET), pharmacotherapy for smoking cessation, and brief monthly follow-up phone contacts by therapists to support the quit attempt. The complete randomization sequence will be generated a priori and performed centrally by the study staff.

Although participants will attend a total of 15 sessions for this study, not all study sessions will include therapy. In the CPT-C and smoking condition, participants will receive 12 sessions of combined PTSD and smoking therapy. The first 50 minutes of each session will be devoted to the randomized therapy and the last 25 minutes will be devoted to the manualized integrated smoking cessation treatment by McFall and Saxon (McFall & Saxon, 2005). Sessions 7 through 12 of the treatment sessions will include 50 minutes of the randomized therapy, and brief (five to ten minutes) check-in regarding smoking relapse prevention and/or renewed quit attempts. In the smoking cessation without concurrent CPT-C condition, there will still be 15 total study sessions, with 6

including therapy for smoking cessation and lasting 25 minutes. If, during the course of treatment, a participant is lost to contact, the study coordinator will send an IRB-approved "no-contact letter" to increase the likelihood that we re-establish contact.

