# **Data Analysis and Hypotheses:**

The following variables will be described for the sample as a whole: minority status, marital status, age, trauma exposure, negative affect level, PTSD symptom severity, nicotine dependence, mean pack years, nicotine cigarette brand, and mean number of cigarettes smoked daily.

Because one of the aims of this study is to assess the efficacy of the combined CPT-C and smoking intervention on smoking cessation, we will analyze these variables to determine whether they change over time.

- Compared to the smoking cessation alone protocol, the smoking cessation + concurrent CPT-C protocol will result in reduced frequency and intensity of PTSD symptoms.
- Compared to the smoking cessation alone protocol, the smoking cessation + concurrent CPT-C protocol will result in reduced depressive symptoms.
- 3) The smoking cessation + concurrent CPT-C protocol will result in decreased smoking rates, relative to published data on VA smoking cessation usual care.
- 4) Greater PTSD symptom reduction during the smoking cessation + concurrent CPT-C treatment will result in longer duration to smoking lapse and relapse.
- 5) Exploratory research question: Will use of automated text messaging as an adjunct to smoking cessation be feasible, and will it impact quit rates and symptom severity?

Hypothesis 1. Compared to the PTSD Coach and smoking cessation protocol, the CPT-C and smoking cessation protocol will result in reduced frequency and intensity of PTSD symptoms. The change in PTSD symptoms over time will be analyzed using repeated-measures ANOVA, utilizing data provided at baseline, post-treatment, and 6-months post-quit. We will evaluate the potential influence of several potential psychosocial covariates on smoking abstinence, including: 1) demographics (age, race, socioeconomic

status), 2) psychiatric variables (PTSD symptom severity, depression, substance abuse/dependence), 3) smoking variables (self-efficacy, motivation to quit, social support, smokers in social group), and 4) treatment process variables (therapeutic alliance, satisfaction with treatment, attendance at sessions, homework adherence).

Hypothesis 2. Compared to the PTSD Coach and smoking cessation protocol, the CPT-C and smoking cessation protocol will result in reduced depressive symptoms. Analysis procedures for Hypothesis 2 will be the same as those used for Hypothesis 1.

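### The Population section gives seventy as the study size but plans recruitment for at least fifty, and nothing in the plan reconciles the two

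*Combined protocol and SAP*

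**What the plan says.** The sample size appears only in the Population section, in two consecutive sentences. The first reads "The proposed study will recruit seventy male and female veterans ages 18 to 75 for participation in the CPT-C and smoking cessation treatment". The second gives its basis as "Based on data from other similar clinical trials run in the Traumatic Stress and Health Research Laboratory" and continues "we estimate that we will need to recruit 120 participants in order to reach an enrollment goal of at least fifty participants".

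Both sentences use the verb recruit, with 70 in one and 120 in the other. Neither defines it.

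The Summary of Inclusion Exclusion Criteria introduces its list with "To be enrolled in this study, participants must have the following characteristics", which ties enrolment to meeting the eligibility criteria and not to finishing the study. The Intervention Protocol section describes two randomised arms ("participants will be randomized to participate in either a 12-session CPT-C with concurrent smoking cessation treatment or a smoking cessation treatment") and gives no allocation ratio. Nowhere do the documents state a number per arm, an expected dropout rate, a significance level, a power or an effect size.

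**The concern.** A reader who wants to know how many veterans the trial will randomise finds two figures, and the recruitment number beside them matches only one. The size governs how precisely the arms can be compared on PTSD and depressive symptoms. It is also the yardstick for judging later whether the trial reached its target. With 70 and at least 50 both on the page, a trial that ends with 50 and one that ends with 70 could each be described as having met the plan. Since no power calculation is given, neither figure can be recovered from other inputs, and a reader cannot tell which one the sponsor relies on.

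**Working it through.** **Inputs, all from the Population section.** 120 to be recruited; an enrolment goal of at least 50; 70 to be recruited for participation in treatment. The recruit-to-enrolled rate is not given.

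**Step 1: the plan's own pair of figures.** Implied yield = 50/120 = 0.417, or 41.7%. Applied back, 120 × 0.417 = 50. This only restates the plan's figures, since the yield comes from the same two numbers. It is the yield that just meets the floor.

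**Step 2: seventy read as the number enrolled.**
- Expected from 120 recruits: 50, which is 70 − 50 = 20 short (20/70 = 29%).
- Yield needed to get 70 from 120: 70/120 = 58.3%, against the implied 41.7%.
- Recruits needed for 70 at the implied yield: 70/0.4167 = 168, which is 168 − 120 = 48 more than planned.

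**Step 3: seventy read as the number recruited.** 70 × 0.4167 = 29 enrolled, which is 50 − 29 = 21 below the floor. This reading also contradicts the 120 in the next sentence directly.

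| Reading of seventy | Recruited | Expected enrolled at 41.7% | Fits 120 recruited for at least 50? |
|---|---|---|---|
| Enrolled, 120 recruited | 120 | 50 | No: 20 short of 70 |
| Enrolled, yield held | 168 | 70 | No: 48 more recruits |
| Recruited | 70 | 29 | No: 21 below the floor |

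**Step 4: the unstated sequence.** 120 recruited, 70 entering treatment and 50 completing would imply entry of 70/120 = 58.3% and retention of 50/70 = 71%. The arithmetic closes, but only if fifty counts completers, and the sentence calls it "an enrollment goal of at least fifty participants".

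**Step 5: what separates 50 from 70 (illustration only).** Assumptions not in the documents: 1:1 allocation, two-sided 5%, 80% power, a t-test at a single time point, no dropout. By the noncentral t distribution, the detectable standardised difference is 0.81 SD with 25 per arm (50 in total) and 0.68 SD with 35 per arm (70 in total). The planned analysis is different: "The change in PTSD symptoms over time will be analyzed using repeated-measures ANOVA, utilizing data provided at baseline, post-treatment, and 6-months post-quit". Correlated repeated measures could make the detectable difference smaller, and dropout would make it larger.

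**The case against.** The strongest reply is that the figures do not exclude one another. At least fifty is a floor, and a trial that enrols 70 satisfies it. That stands: enrolling 70 would breach nothing. It does not explain how 70 would be reached, because the only recruitment number in the plan is tied to fifty.

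A second reply is that the figures are a sequence of 120 recruited, 70 treated and 50 retained. The first sentence does speak of participation in treatment, and the Recruitment section provides for participants who drop out. The sequence may be what the sponsor meant. As worded, though, fifty is an enrolment figure, and the eligibility summary attaches enrolment to meeting the entry criteria. The reading is possible but unstated, and it too would need to be written down.

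A third reply is that 41.7% is not a parameter of the plan. That also stands. It is a ratio of a rounded estimate and a floor, drawn from laboratory data that the documents do not show. The figures of 29 and 168 are therefore conditional on it. The documents also do not say whether recruited means approached, consented or screened.

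A reader might infer something stronger: that seventy refers to the combined-treatment arm alone, since the sentence names that treatment. The documents do not support this. The subject of the sentence is the study, and 70 in one arm would mean about 140 randomised at 1:1, more than the 120 to be recruited.

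**Conclusion.** The point holds as an unreconciled sample size. Taken as worded, seventy fits the stated recruitment plan neither as the number enrolled (20 short from 120 recruits) nor as the number recruited (about 29 enrolled, against a floor of fifty). Both shortfalls rest on the implied yield of 41.7%.

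A reader might go further and infer that the two sizes are mutually exclusive, or that one is a proven arithmetic error. Neither follows: fifty is a minimum, a treated-and-retained sequence cannot be ruled out, and without a power calculation the documents cannot show which number is right. Nor do they give the power of the planned hypothesis tests. The detectable differences of about 0.81 SD and 0.68 SD only indicate that the choice between 50 and 70 matters; they are not the precision of the planned repeated-measures analysis.

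**What to change.** Replace the two sentences in the Population section with one target for the number randomised, in total and per arm, restated to what recruiting 120 supports: about 50 in total at the implied yield. Define recruited and enrolled, and state the expected yield as an assumption with its source.

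If the sponsor meant 120 recruited, 70 treated and 50 completing, write that sequence out with the expected retention of 71%, and stop calling fifty an enrolment goal.

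Either route changes wording only, with no added recruits beyond 120. The downside is that the stated size may look less favourable. Keeping 70 enrolled at the implied yield is a different choice: it would need about 168 recruits, 48 more than planned, with the added time and cost, unless the sponsor can support a yield near 58%.
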